**Table 5. Clinical Laboratory Tests**

Hematology (Central Lab)	Clinical Chemistry a (Central Lab)	Urinalysis b (Central Lab)	Other Laboratory Tests
Hematocrit Hemoglobin RBC count WBC count Neutrophils Bands Lymphocytes Monocytes Basophils Eosinophils Platelet count	BUN Creatinine Total bilirubin INR (reflex only) c ALT AST Alkaline phosphatase CPK Sodium Potassium Chloride Bicarbonate Calcium Inorganic phosphate Uric acid Cholesterol LDL-C HDL-C Total protein Glucose Triglycerides Albumin	Specific gravity Ketones pH Protein Blood Glucose Urobilinogen Bilirubin Leukocytes Nitrites Microscopic examination, if needed	Central Lab Tests: Serum pregnancy (bHCG) test d HBs Ag e HBs Ab e HBc Ab e HBV DNA PCR reflex only e HCV Ab e HCV RNA reflex only e HIV f QuantiFERON-TB Gold g Rheumatoid Factor e Anti-CCP autoantibodies e ANA and dsDNA (reflex) autoantibodies e hs-CRP h IgG and IgM FSH i MRB Panel j Local Lab Tests Urine pregnancy test k ESR

ALT = alanine aminotransferase; AST = aspartate aminotransferase; bHCG = beta human chorionic gonadotropin; BUN = blood urea nitrogen; CCP = cyclic citrullinated peptide; CK-MB = creatine kinase-MB isozymes; CPK = creatine phosphokinase; DNA = deoxyribonucleic acid; ESR = erythrocyte sedimentation rate; HBc Ab = hepatitis B core antibody; HBs Ab = hepatitis B surface antibody; HBs Ag = hepatitis B surface antigen; HBV = hepatitis B virus; HCV Ab = hepatitis C virus antibody; HDL-C = high-density lipoprotein cholesterol; HIV = human immunodeficiency virus; hsCRP = high sensitivity C-reactive protein; IgG = immunoglobulin G; IgM = immunoglobulin M; INR = international normalized ratio; LDL-C = low-density lipoprotein cholesterol; MRB = minimal residual B-cells; PCR = polymerase chain reaction; RBC = red blood cell; RNA = ribonucleic acid; TB = tuberculosis; WBC = white blood cell

- Minimum 8-hour fast. If a subject is not able to fast when necessary, due to unforeseen circumstances, the non-fasting status will be recorded in study source documentation.
- A urine dipstick macroscopic urinalysis will be completed by the central laboratory at all required visits. A microscopic analysis will be performed in the event the dipstick results show leukocytes, nitrite, protein, ketones, or blood greater than negative or glucose greater than normal.

**Table 5. Clinical Laboratory Tests (Continued)**

- c. INR will only be measured if ALT and/or AST > 3 × ULN.
- d. A serum pregnancy test will be performed for all female subjects at the Screening Visit and if postbaseline urine pregnancy test turns positive.
- e. At Screening only.
- f. Anti-HIV Ab will be performed at Screening, unless prohibited by local regulations. The Investigator must discuss any local reporting requirements to local health agencies with the subject. The site will report confirmed positive results to their health agency per local regulations, if necessary. If a subject has a confirmed positive result, the Investigator must discuss with the subject the potential implications to the subject's health and subject should receive or be referred for clinical care promptly. A subject will not be eligible for study participation if test results indicate a positive HIV infection. AbbVie will not receive results from the testing and will not be made aware of any positive result.
- g. If PPD not performed.
- h. The hsCRP results starting from Baseline (Day 1) will not be reported to the Sponsor, Investigator, study site personnel, and the subject.
- i. At screening for female subjects < 55 years old with no menses for ≥ 12 months AND no history of permanent surgical sterilization.
- j. If needed to assess B cell counts in subjects who have recently discontinued rituximab, see Inclusion Criterion 8, Section 5.2.1.
- k. A urine pregnancy test will be performed for all women of childbearing potential at the Baseline Visit prior to the first dose of study drug and at minimum at monthly intervals (either at study visits or at home between scheduled study visits). (for details see Section 5.3.1.1 (Study Procedures).

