**Table 2. Study Activities (Period 1) (Continued)**

- q. For all females of childbearing potential, collect serum for pregnancy test at screening. If serum pregnancy test comes back borderline, a repeat test  $\geq 3$  days later is necessary to document continued lack of positive result (pregnancy is an exclusion criterion). Refer to Section 5.3.1.1 Study Procedures Pregnancy Test for additional details.
- r. For all females of childbearing potential, collect urine for pregnancy test at Baseline and all subsequent visits. If urine pregnancy test (which is performed at the site) is negative, begin or continue dosing. If urine pregnancy test is positive, withhold dosing and perform a serum pregnancy test. Pregnant subjects must discontinue from the study. Refer to Section 5.3.1.1 Study Procedures Pregnancy Test for additional details.
- s. Central lab hsCRP results will remain blinded to the Sponsor, Investigator, study site personnel, and the subject for all visits except Screening. Results of tests such as hsCRP may be blunted in subjects taking a JAK inhibitor, thereby limiting the clinical utility of these tests in the setting of a possible safety assessment or adverse event management. Any local hsCRP or local CRP tests should not be reported to the investigator until treatment allocation is unblinded.
- t. Minimum 8-hour fast. If a subject is not able to fast when necessary, due to unforeseen circumstances, the non-fasting status will be recorded in study source documentation.
- u. A urine dipstick macroscopic urinalysis will be completed by the central laboratory at all required visits. A microscopic analysis will be performed in the event the dipstick results show leukocytes, nitrite, protein, ketones, or blood greater than negative or glucose greater than normal.

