### **Pregnancy Test**

A serum pregnancy test will be performed for all women of childbearing potential at the Screening Visit. The serum pregnancy test will be sent to and performed by the central laboratory. If the serum pregnancy test is positive the subject is considered a screen failure. If the serum pregnancy test is borderline, it should be repeated  $\geq 3$  days later to determine eligibility. If the repeat serum pregnancy test is:

- Positive, the subject is considered a screen failure;
- Negative, the subject can be enrolled into the trial;
- Still borderline  $\geq 3$  days later, this will be considered documentation of continued lack of a positive result and the subject can be enrolled into the study in the absence of clinical suspicion of pregnancy and other pathological causes of borderline results.

In Period 1, a urine pregnancy test will be performed for all women of childbearing potential at the Baseline Visit prior to the first dose of study drug and at all subsequent visits. More frequent pregnancy tests will be performed throughout the study if required per local/country requirements.

- If the baseline urine pregnancy test performed at the site is negative, then dosing with study drug may begin. If the baseline urine pregnancy test performed at the site is positive, dosing with study drug must be withheld and a serum pregnancy test is required. The serum pregnancy test will be sent to and performed by the central laboratory. If the serum pregnancy test is negative, study drug may be started. If the serum pregnancy test is positive, study drug must be withheld and the subject must be discontinued from the study. In the event a pregnancy test comes back borderline, a repeat test is required.
- If a urine pregnancy test at post-baseline is positive, study drug needs to be temporarily discontinued and a serum pregnancy test is required. The serum pregnancy test will be sent to and performed by the central laboratory. If the serum pregnancy test is negative, study drug may be restarted. If the serum pregnancy test is positive, study drug must be permanently discontinued. In

the event a pregnancy test comes back borderline, a repeat test is required ( $\geq 3$  days later) to document continued lack of a positive result.

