In Period 2, for women of childbearing potential, a urine pregnancy test will be performed at all visits and monthly at home between scheduled study visits. The results of the monthly at home tests will be communicated to the site. If a urine pregnancy test is positive, the subject must stop dosing, come in to the clinic and have blood drawn for a serum pregnancy test that will be analyzed at the central laboratory.

At each visit, the study staff should review the pregnancy avoidance recommendations with each subject of childbearing potential and male subjects with a partner of childbearing potential, and document this discussion in the subject's source records.

A pregnant or breastfeeding female will not be eligible for participation in this study or be allowed to continue study drug.

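### Table 5 note k states a monthly minimum for urine pregnancy tests, but the Period 1 schedule leaves three nominal 42-day gaps between Weeks 30 and 48

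*Protocol*

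**What the plan says.** Four places in the protocol govern urine pregnancy testing in women of childbearing potential.

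- **Table 5, note k:** a test before the first dose and then "at minimum at monthly intervals (either at study visits or at home between scheduled study visits". It names no period, and it sends the reader on: "for details see Section 5.3.1.1 (Study Procedures".
- **Section 5.3.1.1, Pregnancy Test:** in Period 1 the test is done "at the Baseline Visit prior to the first dose of study drug and at all subsequent visits". The only provision there for more is conditional: "More frequent pregnancy tests will be performed throughout the study if required per local/country requirements". In Period 2 it is "performed at all visits and monthly at home between scheduled study visits".
- **Table 2, note r (Period 1):** "For all females of childbearing potential, collect urine for pregnancy test at Baseline and all subsequent visits". No home test is mentioned.
- **Table 4, note k (Period 2):** monthly home tests begin at Week 48.

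Protocol Section 5.1 puts the Period 1 visits at Weeks 2, 4, 8, 12, 14, 18, 22, 26, 30, 36, 42 and 48. The window is ±3 days until Week 30 and ±7 days after that.

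**The concern.** Read as written, note k sets a floor that runs from Baseline, and the detailed schedule does not reach that floor once visits become six-weekly. A site that follows Table 2 and Section 5.3.1.1 tests less often than note k says.

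The stake is how long an undetected pregnancy could stay exposed. From Week 26 the remaining placebo subjects move to upadacitinib (Section 5.2.3.3), so every woman still on study drug takes upadacitinib or adalimumab, with background methotrexate. The rationale for the inclusion criteria calls the effect of upadacitinib on pregnancy unknown, and a pregnant subject must stop study drug (Sections 5.4.1 and 6.1.6). The test interval therefore bounds how late the scheduled tests can trigger that stop. The protocol fills the 12-week visit gaps of Period 2 with monthly home tests, and it gives no reason for a wider interval in Weeks 30–48.

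**Working it through.** **Inputs.** Target days are those of Table 2 (Day = 1 + 7 × week) and visit windows those of Section 5.1. The protocol does not define a month; 31 days is assumed as its longest length, with 28 days shown for range.

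**Nominal gaps, Baseline to Week 48:** 14, 14, 28, 28, 14, 28, 28, 28, 28, 42, 42, 42 days. All gaps up to Week 30 are nominally 28 days or less. Exactly three exceed a month.

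| Interval | Target days | Nominal | Permitted range |
|---|---|---|---|
| Weeks 30–36 | 211 to 253 | 42 | 246 − 214 = 32 to 260 − 208 = 52 |
| Weeks 36–42 | 253 to 295 | 42 | 288 − 260 = 28 to 302 − 246 = 56 |
| Weeks 42–48 | 295 to 337 | 42 | 330 − 302 = 28 to 344 − 288 = 56 |

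**Size of the shortfall.**

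- 31-day month: 42 − 31 = 11 days per gap; 3 × 11 = 33; 33/336 = 9.8% of Period 1.
- 28-day month: 42 − 28 = 14 days per gap; 3 × 14 = 42; 42/336 = 12.5%.

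**Can visit windows close the gaps?**

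- Weeks 30–36 always last at least 32 days, so that gap always exceeds 31.
- Weeks 36–48 last at least 330 − 260 = 70 days. This is more than 2 × 31 = 62, so at least one of its two gaps exceeds 31.
- At least two of the three gaps therefore exceed 31 days for any permitted dates.
- Full count: 7 × 15 × 15 × 15 = 23,625 date combinations. In 21,525 all three gaps exceed 31 days, in 2,100 two do, and in none do fewer.
- Weeks 30–48 last at least 330 − 214 = 116 days, and 116/3 = 38.7, so the longest gap is at least 39 days.

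**Before Week 30.** The six 28-day intervals can reach 28 + 3 + 3 = 34 days, but only through the ordinary visit tolerance.

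**With home tests on Days 232, 274 and 316 (Weeks 33, 39 and 45).** Nominal gaps after Week 30 become 21 days. At the visit-window limits the largest are 232 − 208 = 24 for the first interval and 28 for each of the other five (for example 260 − 232). Allowing ±3 days on the home tests as well, they are 27 and 31.

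**The case against.** The strongest reply is that note k is a pointer and not the controlling schedule. It defers to Section 5.3.1.1, which separates the two periods clearly and agrees with Table 2, note r, and Table 4, note k. The summary of changes (Section 1.1) says note k was updated to align with the protocol text and announces no new Period 1 testing. Other Table 5 notes are just as compressed: note d gives serum testing for all female subjects where Section 5.3.1.1 says women of childbearing potential, and note h gives no end to hsCRP blinding where Table 4, note l, does. On this view the mismatch is one of wording.

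Much of that stands. Note k may well be a loose summary of both periods, and a reader should not infer that sites following Table 2 breach a firmly intended rule. Nor do the documents show that six-weekly testing is unsafe, since they set no maximum safe interval. The safeguards are real: highly effective contraception is required (Section 5.2.4), each Period 1 visit has a test, at each visit "the study staff should review the pregnancy avoidance recommendations with each subject of childbearing potential", and local rules or unscheduled visits can add tests.

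What does not stand is that note k's mention of home tests already solves the problem. No Period 1 procedure schedules or reports them, and Appendix C sets no test frequency. The texts still differ, whichever one was intended.

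Two larger figures are also tempting. The three gaps span 126 of 336 days (37.5%), but that counts the part of each gap that meets a monthly rule. The single-gap maxima of 52, 56 and 56 days cannot all occur in one woman: her three gaps total at most 344 − 208 = 136 days.

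**Conclusion.** The inconsistency is real and minor. Note k's stated minimum is missed in three nominal 42-day intervals, each 11 days beyond a 31-day month, 9.8% of Period 1 in total, and visit windows cannot remove it. The size rests on the assumed length of a month and on reading note k literally from Baseline.

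The consequence is limited to possible later detection of a pregnancy on active drug between Weeks 30 and 48. Given the contraception and visit-test requirements the absolute risk should be low, but it cannot be quantified because the number of women of childbearing potential is not given. No endpoint, power or alpha statement is affected.

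**What to change.** **Preferred.** In Section 5.3.1.1 and Table 2 (a new row or note), add one in-home urine test at about each of Weeks 33, 39 and 45 (Days 232, 274 and 316). Use the procedure already written for Period 2: the result goes to the site, and if it is positive "the subject must stop dosing, come in to the clinic and have blood drawn for a serum pregnancy test". Table 4, note k, should cross-refer to it, because a Period 1 procedure belongs in Table 2. Note k of Table 5 should also say that visit windows apply, since intervals before Week 30 can reach 34 days.

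**Minimum.** If the sponsor did not intend monthly testing in Period 1, limit the monthly wording in Table 5, note k, to Period 2. The texts then agree, but the six-week gaps remain.

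**Cost of the preferred fix.** Three home kits per woman of childbearing potential, reporting of the results to the site, and an amendment with ethics committee approval. The documents do not say who supplies the kits.

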### **Hepatitis Screen**

All subjects will be tested for the presence of HBV and HCV at Screening.

#### *Hepatitis B:*

Subjects will be tested for the presence of HBV at screening using the following tests:

[figure not shown]
- HBs Ag (Hepatitis B surface antigen)
- HBc Ab/anti-HBc (Hepatitis B core antibody)
- HBs Ab/anti-HBs (Hepatitis B surface antibody)

A positive result for HBs Ag will be exclusionary.

A negative result for HBs Ag will be tested (automatic reflex testing) for core antibodies (HBc Ab) and surface antibodies (HBs Ab).

- A negative test result for HBc Ab does **not** require HBV DNA PCR qualitative testing and the subject may be enrolled (Figure 4, Scenarios A and B). For a subject who has had a HBV vaccination (should document in the medical history), a positive test result for HBs Ab is expected and the subject may be enrolled (Figure 4, Scenario B).\*
- A positive test result for HBc Ab requires HBV DNA PCR testing (automatic reflex testing) (Figure 4, Scenarios C and D).
  - A positive result for HBV DNA or a result that exceeds detection sensitivity will be exclusionary.
  - A subject with a negative result for HBV DNA may be enrolled.

**Figure 4. Criteria for HBV DNA PCR Qualitative Testing**

\* For subjects who have had a HBV vaccination (should be documented in the medical history), a positive test result for HBs Ab is expected and these subjects may be enrolled.

*Hepatitis C:*

Blood samples for Hepatitis C serology will be obtained at the Screening Visit. A subject will not be eligible for study participation if test results indicate active Hepatitis C (HCV RNA detectable in any subject with anti HCV Ab).

## **HIV**

Subjects with a known history of HIV infection are excluded from study participation. If required by country regulatory authorities to confirm eligibility, subjects should be tested for antibodies to HIV at Screening. This testing is to be done at the central lab. A subject will not be eligible for study participation if test results indicate a positive HIV infection. AbbVie will not receive results from the testing and will not be made aware of any positive result.

## **Randomization/Drug Assignment**

All Screening laboratory results must be reviewed, signed and dated by the Principal Investigator or Sub-investigator prior to the Baseline Visit. Subjects will not be enrolled into the study if laboratory or other Screening result abnormalities are deemed clinically significant by the Principal Investigator or Sub investigator.

Subjects will be eligible for randomization if they continue to meet all of the selection criteria (Section 5.2) at Baseline and are willing to continue in the study.

Subjects will be randomized in a 2:2:1 ratio using interactive response technology (IRT) to receive double-blind study drug in one of the following treatment groups:

- Group 1: Upadacitinib (ABT-494) 15 mg QD (N = 600)
- Group 2: Placebo (N = 600)
- Group 3: ADA (40 mg eow) (N = 300)

Randomization will be stratified by prior bDMARD exposure (yes or no) and geographic region.

See Section 5.5.3 for details.

### **Study Drug Dispensing, Dosing, and Compliance**

Study drug will be dispensed to subjects beginning at Baseline (Day 1) and as specified in [Table 2](#) and [Table 4](#). The first dose of study drug will be administered after all other Baseline (Day 1) procedures are completed. Subjects will maintain a dosing diary for all study drug administered outside of the study visit (i.e., at home) to capture dosing dates and times. At visits specified in [Table 2](#) and [Table 4](#), the site personnel will review and retain a copy of the dosing diary, returned study drug kits, and empty study drug packaging to verify compliance.

All relevant dosing information will be entered into the eCRF at each visit.

ADA/placebo for ADA study drug can be administered to subjects by study site medical staff or designee (subject, friend, family member, or health care professional) during the visit at Baseline. Subjects or a designated family member or friend will be trained to administer study drug at this visit.

(Refer to Section [5.5](#) for additional information).

#### **5.3.1.2 Collection and Handling of Optional Samples for Exploratory Research and Validation Studies**

In Period 1, subjects will have the option to provide samples for exploratory research and validation studies. Subjects may still participate in the main study even if they decide not to participate in this optional exploratory research/validation study.

Exploratory research can help to improve our understanding of how individuals respond to drugs and our ability to predict which subjects would benefit from receiving specific therapies. In addition, exploratory research may help to improve our understanding of how to diagnose and assess/monitor RA by assessing associations between disease characteristics, outcomes data, and biomarkers of interest.

Validation studies, including those related to the development of potential in vitro diagnostic tests, may be carried out retrospectively in order to assess associations between events of interest (i.e., efficacy and/or safety events) and candidate biomarkers.

AbbVie (or people or companies working with AbbVie) will store the biomarker exploratory research/validation studies samples in a secure storage space with adequate measures to protect confidentiality. The samples will be retained while research on upadacitinib (or drugs of this class) or RA and related conditions continues, but for no longer than 20 years after study completion.

#### **DNA Samples for Pharmacogenetic or Epigenetic Analyses**

Whole blood samples for DNA isolation will be collected at the visits indicated in [Table 3](#) from each subject who consents to provide samples for exploratory/validation research. The procedure for obtaining and documenting informed consent is discussed in [Section 9.3](#).

Samples will be shipped frozen to AbbVie or a designated laboratory for DNA extraction and/or long-term storage or analyses. Instructions for the preparation and shipment of the pharmacogenetic and/or epigenetic research samples will be provided in a laboratory manual.

#### **RNA Samples for Transcriptomic and/or Epigenetic Analyses**

Whole blood samples for RNA isolation will be collected at the visits indicated in [Table 3](#) from each subject who consents to provide samples for exploratory/validation research. The procedure for obtaining and documenting informed consent is discussed in [Section 9.3](#).

Samples will be shipped to AbbVie or a designated laboratory for RNA extraction and/or long-term storage or analyses. Instructions for the preparation and shipment of the samples will be provided in a laboratory manual.

## **Serum and Plasma Samples for Systemic Analyses, Including but Not Limited to Proteomic and Metabolomic**

Serum and plasma samples will be collected at the visits indicated in [Table 3](#) from each subject who consents to provide samples for exploratory/validation research. These samples may be used for assay of study drugs if needed. The procedure for obtaining and documenting informed consent is discussed in [Section 9.3](#).

Samples will be shipped to AbbVie or a designated laboratory for long-term storage and/or analyses. Instructions for the preparation and shipment of the samples will be provided in a laboratory manual.

